### 2. Objectives and Hypotheses

Primary Objective:

- To evaluate whether a story-based digital game intervention improves treatment adherence, dietary knowledge, and reduces anxiety in patients undergoing hemodialysis.

Hypotheses:

- H1: Patients receiving the digital game intervention will show higher adherence scores.
- H2: Patients receiving the intervention will demonstrate improved dietary knowledge.
- H3: Anxiety levels will decrease more significantly in the intervention group than in the control group.

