### 4. Statistical Methods

The analysis will follow the intention-to-treat principle. Descriptive statistics will be calculated for all variables. Continuous variables will be presented as mean  $\pm$  standard deviation, and categorical variables as frequencies and percentages.

Between-group comparisons of continuous variables will use the Mann–Whitney U test. Repeated measures within each group will be analyzed using the Friedman test. Post hoc analyses will be conducted using the Wilcoxon signed-rank test with Bonferroni correction where applicable. Chi-square or Fisher's exact tests will be used for categorical data.

Statistical significance will be determined at a two-sided alpha level of 0.05.

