## **6. Assumptions and Adjustments**

Given the small sample size and the ordinal nature of the scales used, non-parametric tests were selected. Multiple testing adjustments will be made using Bonferroni correction. Data will be analyzed using IBM SPSS v26.0.

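### The SAP promises Bonferroni without a family or divisor and fixes neither time point nor score for the three between-arm primary tests, so the significance threshold for a primary claim is ambiguous

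*SAP*

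**What the plan says.** Protocol section 8 names three primary outcomes: an adherence scale, a diet knowledge scale and a state anxiety scale. SAP section 2 attaches one hypothesis to each (H1 to H3).

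On the tests, SAP section 4 states: "Between-group comparisons of continuous variables will use the Mann–Whitney U test". Within arms: "Repeated measures within each group will be analyzed using the Friedman test". It then says: "Post hoc analyses will be conducted using the Wilcoxon signed-rank test with Bonferroni correction where applicable". On the level: "Statistical significance will be determined at a two-sided alpha level of 0.05". It does not say whether that level is per test or per family. Protocol section 9 lists Mann–Whitney and Friedman with no correction attached and applies Bonferroni to the Wilcoxon tests.

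SAP section 6 speaks of multiplicity in general: "Multiple testing adjustments will be made using Bonferroni correction". It does not list the tests that form the family or give the number to divide by.

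On what is compared, H1 reads as a level: "Patients receiving the digital game intervention will show higher adherence scores". H3 reads as a change: "Anxiety levels will decrease more significantly in the intervention group than in the control group". H2 speaks of improvement and could be either. No section supplied gives a measurement schedule, a primary time point or the score to be analysed.

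**The concern.** The question the trial was set up to answer is the difference between arms. The only tests to which either document specifically attaches Bonferroni are pairwise comparisons over time within one arm, and these cannot answer it. Whether the three tests that can answer it are corrected depends on how far one general sentence in SAP section 6 reaches.

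Two open items make this worse. The Friedman test implies several measurement occasions (ordinarily three or more), but none is chosen for the between-arm comparison. The hypotheses also mix a level with a change. Until both are fixed, the number of between-arm primary tests is not known, and a Bonferroni divisor cannot be determined even by a reader who accepts that the correction applies.

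What is at stake is the credibility of a positive result. If the threshold can be settled after the p-values are seen, a reader cannot tell whether a result at, say, p = 0.03 met a pre-specified criterion.

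**Working it through.** **Inputs from the documents.** Three primary outcomes (Protocol section 8); one hypothesis per outcome (SAP section 2); two-sided 0.05 and Mann–Whitney between arms (SAP section 4); Bonferroni with no divisor (SAP section 6). The 0.05 is a chosen level, and no sample size or power is stated, so there is no derived figure to reproduce.

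**Assumptions.** One between-arm test per outcome, with a claim allowed on any one outcome. The correlation r between the three test statistics is not in the documents and is varied below.

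**Reading A: SAP section 6 covers the three between-arm primary tests.**
- Per-test level: 0.05/3 = 0.0167.
- Upper bound on family-wise error, whatever the correlation: 3 × 0.0167 = 0.05.
- If independent: 1 − (1 − 0.0167)³ = 0.049.

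**Reading B: the correction applies only where it is tied to a specific test (Wilcoxon), so each Mann–Whitney test is judged at 0.05.**
- If independent: 1 − (1 − 0.05)³ = 1 − 0.857 = 0.143.
- Upper bound: 3 × 0.05 = 0.15.

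**Effect of correlation.** Three two-sided normal test statistics with common correlation r were simulated with four million draws. The table gives the probability that at least one is significant when no outcome is affected.

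| r (assumed) | Reading A, each at 0.0167 | Reading B, each at 0.05 |
|---|---|---|
| 0 | 4.9% | 14.3% |
| 0.3 | 4.8% | 13.6% |
| 0.5 | 4.4% | 12.5% |
| 0.7 | 3.9% | 10.9% |
| 0.9 | 3.0% | 8.4% |

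Mann–Whitney tests simulated directly at an assumed 30 per arm gave 14.2, 13.8, 12.6, 11.2 and 8.5% at 0.05 for the same correlations, so the normal approximation is adequate here.

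**The disputed zone.** The readings disagree about any primary p-value above 0.0167 and up to 0.05. How often a result lands there depends on sample size and effect, and the documents give neither.

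**Why time point and score belong to the same point.** Reading A reaches 5% only if there is exactly one between-arm test per outcome. If each outcome were tested twice (two occasions, or both final and change), there would be six tests. With a divisor of 3 the bound would be 6 × 0.0167 = 0.10, not 0.05. The divisor follows from the time point and score, and neither is stated.

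**The case against.** The strongest reply is that SAP section 6 already settles the matter. Its sentence is general and carries no qualifier such as the one in section 4. Section 4 has already dealt with the Wilcoxon tests, so confining section 6 to them would make it redundant. The natural reading is a general commitment that reaches the primary comparisons. This stands, and it is why no claim of an uncontrolled error rate is made here. It does not close the gap. Protocol section 9 leaves Mann–Whitney uncorrected, and a commitment without a family or divisor does not fix a threshold.

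It can also be said that statistician blinding (Protocol section 5) limits a choice made after the fact. That is a partial safeguard: it hinders choosing a favourable direction, but p-values can be seen without knowing which arm is which.

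Three stronger readings are tempting and should not be drawn.
- **That the plan runs at 14% error.** This holds only under Reading B, which is the less natural of the two.
- **That the error is higher still, because each outcome will be tested at several visits or on both scores.** No section proposes such between-arm analyses. The documents are silent on the point, and silence is not a plan to do it.
- **That success might require all three outcomes, so that no correction is needed.** The conjunction in the SAP objective is an ordinary list. Protocol section 4 gives three separate objectives and H1 to H3 stand apart. Nothing refers to joint success.

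**Conclusion.** The point holds as an incompletely specified correction, and it should be fixed. Family-wise error for the primary claims is at most 5% if SAP section 6 covers exactly one between-arm test per outcome. It is 14.3% for independent outcomes (12.5% at r = 0.5) if the correction is confined to the tests to which it is tied and any one outcome supports a claim. The lower figure of about 8% needs a correlation near 0.9 between three different constructs; it is a sensitivity limit, not an expectation. The correlations are assumptions. The values 0.0167, 5% and 14.3% need only the three outcomes, the 0.05 level and, for 14.3%, independence. The documents do not show that the error is inflated. They do leave the threshold for a primary claim, and the variable to which it applies, open to choice.

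**What to change.** In SAP sections 4 and 6 and Protocol section 9:

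1. Define the confirmatory family as exactly three between-arm tests, one per primary outcome, at one named time point and on one named score (final or change).
2. Allow a separate claim for each outcome, in line with H1 to H3.
3. Control two-sided family-wise error at 0.05 across that family, preferably by Holm. Holm controls the same error as the promised Bonferroni and is never less powerful. Bonferroni at 0.05/3 is also acceptable; the family, time point and score are the necessary part.
4. State that within-arm Friedman and Wilcoxon results cannot support a between-arm primary claim.

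SAP section 3 describes randomization as already done, so the revision should be dated before the statistician is unblinded. If unblinding has already happened, report the rule as added afterwards.

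The cost is wording, plus lower power per outcome than unadjusted tests at 0.05. The SAP says only this about size: "Given the small sample size and the ordinal nature of the scales used, non-parametric tests were selected". The loss therefore cannot be computed without assumptions. As an illustration, take a 0.5 SD effect, correlation 0.3 and untied normal data, all assumed. Simulated Mann–Whitney power per improved outcome is then:

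| Assumed n per arm | Unadjusted 0.05 | Bonferroni 0.0167 | Holm, all three improve |
|---|---|---|---|
| 20 | 32% | 18% | 20% |
| 30 | 46% | 29% | 34% |
| 40 | 58% | 40% | 47% |
| 50 | 68% | 50% | 58% |

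If only one outcome improves, Holm gains almost nothing over Bonferroni. The scales are ordinal, so ties would shift these figures somewhat.

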## **5. Variables and Measurement Tools**

- Adherence: Measured using the End-Stage Renal Disease Adherence Scale.
- Dietary Knowledge: Assessed via the Hemodialysis Patients' Diet Knowledge Scale.
- Anxiety: Measured using the State Anxiety Scale.
- Game Experience: Evaluated using the GAMEX Scale in the intervention group.

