Study Protocol

Official Title: A Story-Based Digital Game to Reduce Anxiety and Improve Treatment Compliance in Hemodialysis Patients: A Randomized Controlled Trial

NCT Number: To be assigned

Ethics Committee Approval Number: E.888577

Study Period: March 2025 – April 2025

Study Protocol

Title: A Story-Based Digital Game to Reduce Anxiety and Improve Treatment Compliance in Hemodialysis Patients

Protocol Version: 1.0

Protocol Date: March 1, 2025

Principal Investigator(s): [name] [name], Assoc. [name]

Institution: Suleyman Demirel University, Department of Nursing

Sponsor: Suleyman Demirel University BAP Coordination Unit

1. Project and Study Dates

Project Duration (BAP-Funded): January 3, 2025 – June 17, 2025

Study Implementation Dates: March 1, 2025 – April 30, 2025

2. Ethical Approval

The study protocol was reviewed and approved by the Ethics Committee of Suleyman Demirel

Ethics Approval Number: E.888577

Ethics Approval Date: 11.15.2024

3. Background and Rationale

Hemodialysis patients often face psychological stress, low adherence, and dietary mismanagement. This study introduces a story-based digital game to educate and emotionally support patients during dialysis sessions.

4. Objectives

- To evaluate the impact of a digital game on treatment adherence
- To assess improvements in dietary knowledge
- To determine reductions in anxiety levels among participants

5. Study Design

This is a single-center, single-blinded randomized controlled trial. Participants are assigned to either the intervention (digital game) group or control (standard care) group. Sessions were separated to prevent contamination, and the statistician was blinded to group assignment.

6. Study Population

Inclusion Criteria:

- Age 18–80 years
- At least 6 months on hemodialysis
- Literate
- Consent provided

Exclusion Criteria:

- Cognitive impairment or refusal to consent

7. Intervention Description

The digital game features a fictional character beginning dialysis. Patients mentor this character through challenges, reinforcing their own knowledge on diet, fluid management, and self-care. Each session lasts 10–15 minutes.

8. Outcome Measures

Primary:

- End-Stage Renal Disease Adherence Scale
- Hemodialysis Patients' Diet Knowledge Scale
- State Anxiety Scale

Secondary:

- Game Experience Questionnaire (GAMEX)

9. Statistical Analysis

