### 3. Study Design Summary

This study follows a single-center, single-blinded, randomized controlled design with two parallel arms: an intervention group and a control group. Patients were randomized (1:1) to either group.

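### Does collecting GAMEX only in the game arm undo the statistician's blind?

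*SAP*

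**What the plan says.** Protocol section 5 calls the trial single-blinded and says: "Sessions were separated to prevent contamination, and the statistician was blinded to group assignment". The statistician is the only party that either document names as blinded. SAP section 3 repeats the label without naming anyone: "This study follows a single-center, single-blinded, randomized controlled design with two parallel arms".

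GAMEX is the one secondary outcome in Protocol section 8. SAP section 5 restricts it to one arm: "Game Experience: Evaluated using the GAMEX Scale in the intervention group". SAP section 4 states that "Descriptive statistics will be calculated for all variables" and makes no exception for GAMEX.

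The between-arm test is Mann–Whitney, two-sided at 0.05 (SAP section 4). SAP section 6 adds that multiple testing will be handled by Bonferroni correction. Neither document mentions coded arm labels, file structure, database lock or the order of analyses. SAP text preceding section 1 was not available for this check.

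**The concern.** A scale completed in one arm only is a label for that arm. If the statistician opens a file in which some patients have a GAMEX score and others have none, the allocation is visible, and A/B codes do not help. The statistician's blind is the only one described, so losing it would leave the single-blinded label without content.

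The blind would also have some work to do. The tests are named, but the SAP fixes neither the visit nor the score (value or change) for the Mann–Whitney comparisons. One hypothesis reads "H1: Patients receiving the digital game intervention will show higher adherence scores", which suggests a value. Another reads "H3: Anxiety levels will decrease more significantly in the intervention group than in the control group", which suggests a change. The line "Repeated measures within each group will be analyzed using the Friedman test", with post hoc pairwise tests, implies three or more time points. An analyst who knew the arms could settle these choices in favour of the game.

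**Working it through.** **1. Would GAMEX reveal the arm if it were in the file?** Yes. Allocation is 1:1 (SAP section 3). Let c be the share of game-arm patients with a score (assumed; the documents give no figure).

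- P(game | score present) = 1.
- P(control | score absent) = 0.5 / [0.5 + 0.5(1 − c)] = 1/(2 − c).
- Share of all patients classified correctly = 0.5 + 0.5c = (1 + c)/2.

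| c | P(control given no score) | Classified correctly |
|---|---|---|
| 100% | 1.00 | 100% |
| 90% | 0.91 | 95% |
| 80% | 0.83 | 90% |
| 50% | 0.67 | 75% |

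Under A/B codes, a single score identifies the game code, whatever c is.

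**2. Do the documents put GAMEX in that file before the primary tests?** No. The sentence on descriptive statistics covers all variables but sets no order, no file and no analyst. GAMEX has no control-arm values, so it cannot enter a between-arm test. The Mann–Whitney, Friedman and Wilcoxon tests on the three primary scales can all be run on coded arms without it. A plan that states the blind can be followed as written by summarising GAMEX afterwards.

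**3. How much would knowledge of the arms change?** The documents give no sample size or correlation, so this is an illustration. Assumptions:

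- no true effect, one outcome, n = 20, 30 or 50 per arm;
- correlation between time points 0.3, 0.5 or 0.7;
- baseline plus two follow-up visits, the minimum for a Friedman test if one time point is baseline;
- 2 visits × 2 scores (value, change) = 4 versions of the Mann–Whitney z;
- 20,000 simulated trials per setting.

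Two selection rules are compared. With arms known, the analyst takes the version most favourable to the game. With arms masked, the analyst takes the version with the largest |z|.

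| Result | Arms known | Arms masked |
|---|---|---|
| P(z > 1.96), favouring the game | 7.8%–8.7% | 7.6%–8.6% |
| P(\|z\| > 1.96), either direction | about 8% | about 16% |

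Within a setting, the first row differs by at most 0.16 percentage points. Both rules raise the rate from a nominal 2.5% to about 8%, so the inflation comes from choosing among four versions, not from knowing the arms. The second row does not make masking harmful. It shows that the masked rule also selects results against the game, so comparing these two rules does not measure what masking protects.

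**4. With the Bonferroni correction.** The family is not defined in the SAP. If it is the three primary outcomes (assumed), then 0.05/3 = 0.0167 two-sided and the critical value is 2.394. The rate favouring the game is then 2.5% to 3.0% under either rule, and the difference is at most 0.04 percentage points.

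**The case for a change.** The strongest case for a change has three parts. First, the mechanism is a matter of logic: coding alone cannot protect the blind if GAMEX is in the file, and the plan does not require it to be held back. A reader therefore cannot verify the single-blinded label. Second, masking does prevent selection in one direction. With arms known, the chosen version is significantly against the game in at most 0.03% of simulated trials, compared with 7.9% to 8.4% when masked, and the mean z moves by about 0.8 instead of about 0. Third, the remedy is cheap: a separate file and two or three sentences.

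The first part stands as a description of what is unwritten. It does not show that the blind fails, because the Protocol asserts the blind and nothing contradicts it. The second part is correct arithmetic on an assumed rule. The maximum of four correlated null statistics has a positive mean, and the largest |z| has mean zero by symmetry. The 0.8 therefore measures an analyst who always picks the most favourable version, and the documents give no reason to expect one. The third part is true, but a separate GAMEX file would leave all four versions open. Naming the visit and the score would remove the selection, masked or not.

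**Conclusion.** No change to the plan follows. GAMEX would reveal the arms if it were in the file used for the primary tests, but the documents do not say that it is, and no between-arm analysis calls for it. This is a gap in data-handling detail that an analyst who honours the stated blind fills by summarising GAMEX after the primary comparisons.

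The documents do not allow the effect to be quantified for this trial. Under the assumptions above, knowing the arms changes false positives favouring the game by less than 0.2 percentage points, and by at most 0.04 points if Bonferroni covers the three primary outcomes. Masking the statistician also does nothing about patients knowing whether they play the game.

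Two limits apply. That the statistician is the party meant by single-blinded is an inference from Protocol section 5, which does not define the term; it is a reasonable one, so the bare label in SAP section 3 does no harm. And the unspecified visit and score for the Mann–Whitney tests is a real opening, but it should be judged on its own.

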## **6. Assumptions and Adjustments**

Given the small sample size and the ordinal nature of the scales used, non-parametric tests were selected. Multiple testing adjustments will be made using Bonferroni correction. Data will be analyzed using IBM SPSS v26.0.

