Data will be analyzed per the Statistical Analysis Plan (SAP). Non-parametric methods (Mann-Whitney U, Friedman test) and Bonferroni-corrected Wilcoxon tests will be used. SPSS v26.0 will be employed.

10. Informed Consent and Confidentiality

Informed consent will be obtained from all participants prior to enrollment. Participant confidentiality will be ensured. All data will be anonymized.

11. Monitoring and Reporting

Adverse events will be monitored throughout the study. All protocol deviations and issues will be documented and reported.

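### SAP 6 names single-step Bonferroni for multiple testing; Holm gives the same guaranteed 0.05 bound and never rejects less, though the size of the gain depends on which tests the correction covers

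*SAP*

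**What the plan says.** SAP 6 has one general sentence on multiplicity: "Multiple testing adjustments will be made using Bonferroni correction". It gives no step-down rule, family or divisor. The same section describes the sample as small but gives no number.

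Two other places tie Bonferroni to a particular test. SAP 4: "Post hoc analyses will be conducted using the Wilcoxon signed-rank test with Bonferroni correction where applicable". Protocol 9: "Bonferroni-corrected Wilcoxon tests will be used". In both, the test is the Wilcoxon post hoc comparison.

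SAP 4 assigns the between-arm comparisons to another test, with no correction mentioned beside it: "Between-group comparisons of continuous variables will use the Mann–Whitney U test". The level is set once: "Statistical significance will be determined at a two-sided alpha level of 0.05".

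The primary objective in SAP 2 asks whether the game "improves treatment adherence, dietary knowledge, and reduces anxiety in patients undergoing hemodialysis". Protocol 8 lists the three matching scales as primary. SAP 2 then states H1, H2 and H3 separately and does not say whether success needs all three or any one.

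**The concern.** Single-step Bonferroni holds each of m tests to 0.05/m, whatever the other tests show. Holm orders the p-values and compares the smallest with 0.05/m, the next with 0.05/(m−1), and so on, stopping at the first failure. Both guarantee a family-wise error of at most 0.05 under any dependence. Holm needs no assumption that Bonferroni does not, and it cannot lose a rejection that Bonferroni makes.

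Bonferroni's cost falls on the second and third true effects, which must still clear the strictest threshold after the first has been shown. The primary objective here has three parts and the sample is small, so any power lost this way matters and can be recovered without more patients.

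**Working it through.** **Inputs from the documents.** Two-sided alpha 0.05 (SAP 4); Bonferroni (SAP 6); three primary hypotheses (SAP 2, Protocol 8); Mann–Whitney U between arms (SAP 4).

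**Inputs assumed.** The documents give no sample size, effect size, target power or correlation between scales, so there is no plan figure to reproduce. Assumed: m = 3, single-test power at 0.05 of 30% or 80%, correlation 0 to 0.5, and normal test statistics.

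**1. Thresholds.** Bonferroni: 0.05/3 = 0.0167 for every test. Holm: 0.05/3 = 0.0167, 0.05/2 = 0.025, 0.05/1 = 0.05 for the ordered p-values.

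**2. Error rate.** With three independent true nulls, Bonferroni gives 1 − (1 − 0.0167)³ = 4.9%, and so does Holm. With no correction the rate is 1 − 0.95³ = 14.3%. When two effects are very large and the third is null, the realised rate on that third test is about 5.0% under Holm and 1.7% under Bonferroni. The guarantee is the same; the realised rate need not be.

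**3. Per-test power under Bonferroni, 80% case.** Mean of the test statistic: 1.960 + 0.842 = 2.802. Critical value at two-sided 0.0167: 2.394. Power = Φ(2.802 − 2.394) = Φ(0.408) = 65.8%.

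**4. All three shown, independent tests, by hand.** The chance that p is at most 0.0167 is A = 0.6582. The chance that p is at most 0.025 is Φ(2.802 − 2.241) = 0.7123, so B = 0.7123 − 0.6582 = 0.0541 falls between 0.0167 and 0.025. C = 0.80 − 0.7123 = 0.0877 falls between 0.025 and 0.05.
- Bonferroni: A³ = 0.285.
- Holm needs at least one A and at most one C: A³ + 3A²(B + C) + 3AB² + 6ABC = 0.285 + 0.184 + 0.006 + 0.019 = 0.494.
- No correction: 0.80³ = 0.512.

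**5. Simulation, three equal true effects, 80% single-test power.**

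| Correlation | Per test, Bonferroni | Per test, Holm | All three, Bonferroni | All three, Holm | All three, unadjusted |
|---|---|---|---|---|---|
| 0 | 65.8% | 75.0% | 28.5% | 49.4% | 51.2% |
| 0.3 | 65.8% | 74.1% | 36.4% | 55.2% | 57.0% |
| 0.5 | 65.8% | 73.5% | 41.7% | 59.1% | 61.1% |

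Power for at least one rejection is identical under Bonferroni and Holm (for example 91% at correlation 0.3), because both start at 0.0167. No simulated trial had a Bonferroni rejection that Holm missed.

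**6. Less favourable cases, correlation 0 to 0.5.**
- 30% single-test power, three real effects: per test 17% to 19–20%; all three 0.5–4% to 2–9%.
- 80% power, two real effects and one null: per test on the real effects 66% to 69–70%.
- 80% power, one real effect and two nulls: 66% under both.

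**7. If SAP 6 adds nothing to SAP 4.** The three Mann–Whitney tests would then each stand at 0.05. Putting Holm on them lowers per-test power from 80% to about 74–75%, and all-three power from 51–61% to 49–59%. In return the family-wise error falls from up to 14.3% (independent true nulls) to at most 5%.

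**The case against.** The strongest objection is that the power figures assume a family the documents do not define. Wherever Bonferroni is tied to a named test, that test is the Wilcoxon. The SAP 6 sentence may extend the correction to the between-arm tests or may only restate SAP 4. This stands as a condition on the size of the gain. It does not touch the dominance result, which holds for any family, including the Wilcoxon comparisons.

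A second objection is that showing all three is not a stated success rule. If all three were required, each could be tested at 0.05 with no correction, which slightly beats Holm (57.0% against 55.2% at correlation 0.3). If any one sufficed, Holm would gain nothing. This also stands. Because H1 to H3 are listed separately, per-test power is the more neutral measure, and there the best case is a gain of about 8 to 9 points.

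A reader might infer more than the documents support:
- That the plan is in error. Bonferroni is valid and was named in advance; this is a matter of efficiency.
- That the primary analysis will certainly gain 8 points or more per test. That needs the broad reading of SAP 6, several real effects and adequate power, none of which the documents establish.
- That the two procedures have equal family-wise error. Only the 0.05 bound is shared.

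**Conclusion.** The point holds as a low-cost improvement. For whatever family the correction covers, Bonferroni is dominated by Holm; that part is exact and needs no assumption about this trial.

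The size is conditional. On the plain reading of SAP 6, with m = 3, equal true effects, 80% single-test power and correlation 0 to 0.5, per-test power rises from about 66% to 74–75%, and the chance of showing all three from 29–42% to 49–59%. At 30% power, or with only two real effects, the per-test gain is about 2 to 4 points; with one real effect it is negligible. On the narrow reading the gain is confined to the Wilcoxon comparisons, and using Holm on the primary tests becomes a purchase of error control rather than of power. Since the sample is small and its size unstated, the low-power case cannot be ruled out.

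**What to change.** Make these changes before anyone sees results by arm, since they relax a rejection rule:
- SAP 6: name the three between-arm Mann–Whitney tests (adherence, dietary knowledge, anxiety) as one family, tested by Holm at family-wise two-sided 0.05, with ordered p-values against 0.0167, 0.025 and 0.05. This also settles what the correction covers.
- SAP 4 and Protocol 9: use Holm in place of Bonferroni for the post hoc Wilcoxon comparisons.
- Report Holm-adjusted p-values: 3p for the smallest, 2p for the next and p for the largest, each raised where necessary to the value before it and capped at 1.

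The cost is a short wording change in three places and sorting the p-values; no extra patients or data are needed. The drawback is that Holm has no simple matching simultaneous confidence intervals. The SAP plans no intervals, so little is lost; any that are reported should be labelled unadjusted. If the sponsor intended the primary tests to stand uncorrected, the power cost in step 7 should be accepted knowingly.
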